TITLE	A Phase I/II Trial Of Temozolomide And Hypofractionated Radiotherapy In The Treatment Of Supratentorial Glioblastoma Multiforme
STUDY PHASE	I/II
INDICATION	Newly diagnosed, histologically confirmed supratentorial GBM.
PRIMARY OBJECTIVES	Phase I - Primary Objective Determine the maximum tolerated dose (MTD) of hypofractionated radiotherapy given in 5 fractions with temozolomide for the treatment of glioblastoma multiforme.
SECONDARY OBJECTIVES	Determine the short- and long-term adverse effects. Determine the radiographic response rate. Determine the overall survival rate. Perform patterns of failure analysis. Assess quality of life during treatment.
HYPOTHESES	Five fraction stereotactic radiosurgery (SRS) with concurrent temozolomide will be well-tolerated; the duration of radiotherapy can safely be shortened to 5 treatments without compromising the local control or overall survival rates.
STUDY DESIGN	Phase I: The MTD for five-fraction SRS concurrent with temozolomide will be determined using a 3+3 study design.
PRIMARY ENDPOINTS AND SECONDARY ENDPOINTS	Phase I Primary endpoint The MTD and DLT of hypofractionated radiotherapy with temozolomide will be determined. Secondary endpoints The short- and long-term adverse effects will be determined. The overall survival rate will be calculated. Patterns of failure analysis will be performed. Health related quality of life will be measured.
SAMPLE SIZE BY TREATMENT GROUP	Three patients will be enrolled per dose level per arm. The maximum number of patients

	needed for the phase I study will depend on the number of dose levels reached. If all 4 dose levels are reached, the maximum number of patients will be 15 per arm.

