4.3 Radiation Therapy

1.1.1. Dose specifications/escalation

Radiation will be delivered in five fractions. Provided that the MTD has not been reached, the total dose will be increased as follows:

Dose Level	Dose Per Fraction (Gy)	Total Dose (Gy)
1	5	25
2	6	30
3	7	35
4	8	40

There will be 2 arms to this study:

Arm	PTV volume (cm ³)
1	< 60
2	60-150

A minimum observation period of 30 days following radiotherapy is required prior to proceeding with the next higher dose level.

Common Terminology Criteria for Adverse Events (CTCAE) v4.0 will be used to grade adverse events:

(<http://evs.nci.nih.gov/ftp1/CTCAE/About.html>)

A dose limiting toxicity (DLT) is defined as a treatment related grade 3 - 5 CNS toxicity. Acute toxicity is defined as occurring within <30 days of the end of

radiotherapy. Late toxicity is defined as occurring ≥ 30 days of the end of radiotherapy. The highest dose achieved with an acceptable level of toxicity will be considered the MTD. The highest dose level allowed in this study is 40 Gy. The occurrence of late toxicities will be continuously monitored. If a late DLT occurs in 2 patients at a certain dose level after the radiation dose had already been escalated to the next level, the MTD will be backtracked to the level below the one at which the DLTs occurred.

Dose escalation will follow a traditional 3 + 3 design:

Number of Patients with DLT at a Given Dose Level	Escalation Decision Rule
0 out of 3	Enter 3 patients at the next dose level.
1 out of 3	Enter at least 3 more patients at the current dose level. 
 • If 0 of these 3 experiences a DLT (i.e., 1 out of 6), then proceed to next dose level. • If 1 or more of these 6 experiences a DLT (2 or more out of 6), then dose escalation will be stopped. Three additional patients will be entered at the next lower dose level if only 3 patients were previously entered.
>1 out of 3	Dose escalation will be stopped. Three additional patients will be entered at the next lower dose level if only 3 patients were previously entered.

Should a patient not be evaluable at 30 days (due to death unrelated to protocol treatment or loss to follow-up or discontinuation of the protocol follow-up per patient preference), then additional patients may be enrolled on each arm such that at least 3 are evaluable for DLT.

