11. STATISTICAL CONSIDERATIONS

11.1 Endpoints

11.1.1 Phase I Primary endpoint

The MTD and DLT of hypofractionated radiotherapy with temozolomide will be determined.

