11.2 Sample Size

11.2.1 Accrual estimates

Three patients minimum enrolled per dose level, plus 3 additional at the dose level of the MTD. The maximum number of patients needed for the phase I study will depend on the number of dose levels reached. If all four dose levels are reached, the maximum number of patients will be 15 per arm.

REFERENCES

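### The stop bullet for an expanded 3+3 cohort counts DLTs among the wrong patients, so at 1 DLT in 6 it contradicts the proceed bullet and its own parenthesis (minor wording error, in both escalation tables)

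*Combined protocol and SAP*

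**What the plan says.** Section 4.3 (subsection 1.1.1, Dose specifications/escalation) introduces its table with "Dose escalation will follow a traditional 3 + 3 design". The row for 1 DLT among the first three patients opens with "Enter at least 3 more patients at the current dose level" and then gives two bullets:

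- Proceed: "If 0 of these 3 experiences a DLT (i.e., 1 out of 6), then proceed to next dose level".
- Stop: "If 1 or more of these 6 experiences a DLT (2 or more out of 6), then dose escalation will be stopped".

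Section 10.2 (Stopping rules) repeats the row with the same two bullets. Elsewhere the acute escalation rule is only named, not spelled out: the synopsis says "The MTD for five-fraction SRS concurrent with temozolomide will be determined using a 3+3 study design", and section 11.1.1 gives the primary endpoint as "The MTD and DLT of hypofractionated radiotherapy with temozolomide will be determined". Section 11.2.1 gives patient numbers but no decision thresholds.

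**The concern.** The row is reached only after one of the first three patients has had a DLT. That patient is one of the six, so the condition in the main clause of the stop bullet is always met and cannot separate stopping from proceeding. Read literally, every expanded cohort would stop, including the one that the bullet above sends to the next level. The clause also gives a different threshold from the parenthesis in its own sentence: 1 of 6 against 2 of 6.

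The rule decides whether the next patients receive a higher brain dose, in steps from 25 to 40 Gy and separately in each of two volume arms, and it leads to the MTD, which is the primary endpoint. The two tables are the only places that state the counts for acute escalation. Because both carry the same words, neither corrects the other.

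**Working it through.** **Inputs.** From sections 4.3 and 10.2: 1 DLT in the first 3 patients; 3 patients added (the smallest expansion that the row allows); proceed if none of the added 3 has a DLT; stop at the count in the parenthesis, 2 or more of 6. Assumed, because the documents give none: a true DLT risk p of 5%, 10%, 20% or 30%, with patients independent.

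**Step 1: try to reproduce the plan's own threshold.** Let k be the number of DLTs among the 3 added patients, so the total is 1 + k of 6.

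| k | Total of 6 | Proceed bullet (k = 0) | Stop, main clause as written (total ≥ 1) | Stop, parenthesis (total ≥ 2) | Stop, counted in the added 3 (k ≥ 1) |
|---|---|---|---|---|---|
| 0 | 1 | proceed | **stop** | no stop | no stop |
| 1 | 2 | – | stop | stop | stop |
| 2 | 3 | – | stop | stop | stop |
| 3 | 4 | – | stop | stop | stop |

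The main clause as written does not give the stated threshold. Counting among the added 3 gives it for every k and is the exact complement of the proceed bullet. The clauses disagree in one row only, k = 0.

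**Step 2: how often that outcome arises.**

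- Exactly 1 DLT in the first 3: 3p(1−p)².
- None in the next 3: (1−p)³.
- Both, per dose level: 3p(1−p)² × (1−p)³ = 3p(1−p)⁵.
- Given that the row has been reached, the share ending at 1 of 6: (1−p)³.

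At p = 0.20: 3 × 0.20 × 0.80⁵ = 0.6 × 0.32768 = 0.197, and 0.80³ = 0.512.

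**Step 3: upper bound on the effect.**

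- Chance of passing a level under the intended rule: (1−p)³ + 3p(1−p)⁵.
- Chance if the main clause were always obeyed literally, so that only 0 of 3 proceeds: (1−p)³.

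At p = 0.20: 0.512 + 0.197 = 0.709, against 0.512.

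| Assumed DLT risk | Ends at exactly 1 of 6, per level | Same, given 1 of first 3 | Pass a level, intended | Pass a level, literal |
|---|---|---|---|---|
| 5% | 0.116 | 0.857 | 0.973 | 0.857 |
| 10% | 0.177 | 0.729 | 0.906 | 0.729 |
| 20% | 0.197 | 0.512 | 0.709 | 0.512 |
| 30% | 0.151 | 0.343 | 0.494 | 0.343 |

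The third and last columns are equal because both are the probability of no DLT in three patients. The probability in the second column peaks at p = 1/6, where it is 3 × (1/6) × (5/6)⁵ = 0.201.

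**The case against.** The strongest reply is that the row resolves the conflict itself. For the one disputed outcome a specific bullet says proceed, the stop bullet's parenthesis is not met, and the lead-in names the traditional design. No second workable rule competes, so staff are unlikely to misapply it, and a misreading would err towards stopping. No sample size or analysis depends on the slip. All of this stands, and it is why the point is minor. It does not make the clause correct: a dose-escalation rule should not require the reader to choose between a clause and its parenthesis.

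The probabilities are also open to challenge. The risks are assumed, and the passing figures hold only if someone ignores both the parenthesis and the preceding bullet. That is fair. The figures show that 1 of 6 is an ordinary outcome and put a ceiling on the effect; they do not predict errors.

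Third, the documents cannot show which digit is wrong. Keeping *these 6* and raising the count from 1 to 2 would repair the sentence equally well. This also stands. Counting among the added three is preferred only because it parallels the bullet above.

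Finally, both sections contain another count that affects the MTD: late DLTs in two patients move it down a level. That is a separate rule and does not settle the acute threshold.

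**Conclusion.** The concern holds as a minor inconsistency. In both tables the main clause of the stop bullet is wrong as written: it is always true in the row where it stands, and at 1 of 6 it contradicts the proceed bullet and its own parenthesis. The intended threshold, 2 or more of 6, is clear, so this is a wording error and not a design flaw.

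The disputed outcome has a probability of about 12% to 20% per dose level over assumed DLT risks of 5% to 30%. A consistently literal reading would lower the chance of passing a level by the same amounts, since the difference between the two passing probabilities is exactly 3p(1−p)⁵. These figures rest on the assumed risks, on independent patients and on exactly 3 added patients. The logical contradiction needs none of the probability assumptions.

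**What to change.** In the stop bullet of both tables (sections 4.3 and 10.2), change *these 6* to *these 3* and leave the parenthesis as it is. Stopping then requires at least one DLT among the three added patients, which is 2 or more of 6 in total. Setting the count to 2 or more of the six would do equally well; whichever is chosen, use the same wording in both tables.

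The cost is one digit in each of two tables, with no added patients, time or procedures.

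The row allows an expansion of more than three patients, and neither the present nor the corrected wording says what to do then. This correction leaves that case open.

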1.1.2. Technical factors

Treatment shall be delivered using the Trilogy™ or TrueBeam Linear Accelerator (Varian Medical Systems, Palo Alto, CA) or the CyberKnife™ Robotic Radiosurgery System (Accuray, Sunnyvale, CA).

1.1.3. Localization, simulation, and immobilization

The patient shall be treated in the supine position. An aquaplast head mask will be used to ensure adequate immobilization during therapy.

1.1.4. Target Definition

1.1.4.1. Gross Tumor Volume (GTV)

The gross tumor volume (GTV) will be contoured using the post-operative contrast-enhanced MRI and is defined depending on the type of resection as follows:

- Gross total resection: GTV = tumor resection cavity;
- Partial resection: GTV = residual enhancing tumor plus resection cavity;
- Biopsy only: GTV = enhancing tumor only.

1.1.4.2. Clinical Tumor Volume (CTV)

The clinical tumor volume (CTV) is defined as GTV plus a 0.5 cm margin. This margin may be as small as 0 mm near structures which represent an anatomic border for tumor spread (e.g., falx, calvarium, tentorium). No attempt will be made to include a T2 or FLAIR signal.

1.1.4.3. Planning Target Volume (PTV)

The planning target volume (PTV) is the same as the CTV, without additional margin.

1.1.5. Radiation Dosimetry

- 1.1.5.1. The prescription isodose line shall cover at least 90%, with a goal of at least 95% of the PTV, typically with 10-30% heterogeneity (i.e., the prescription isodose line shall be at 70-90%). The PTV coverage may be lower than 95% in order to meet the dose constraints of critical structures. The conformity indices should be between 1.0 and 1.75.

1.1.6. Critical Structures

Critical normal structures (e.g., optic apparatus, brain stem) will be contoured and their doses minimized. Maximum doses to critical structures are as follows:

- 1.1.6.1. Optic nerves and optic chiasm: 98% of volume to receive <27.5 Gy in 5 fractions. This value is radiobiologically equivalent to 47 Gy in 2 Gy fractions.
- 1.1.6.2. Brain Stem: 98% of volume to receive <30 Gy in 5 fractions. This value is radiobiologically equivalent to 54 Gy in 2 Gy fractions.

1.1.6.3. The radiation isodose line coverage of the PTV shall be decreased in order to meet these dose limits.

4.4 Drug therapy

1.2.6. Temozolomide

Temozolomide (3,4-dihydro-3-methyl-4-oxoimidazo[5,1-d]-*as*-tetrazine-8-carboxamide). At physiologic pH, temozolomide undergoes spontaneous hydrolysis to the active compound MTIC (3-methyl-(triazen-1-yl)imidazole-4-carboxamide). MTIC is thought to kill cells by alkylation of DNA.

1.2.7. Dose definition and administration

Oral temozolomide (75 mg/m²/day) will be administered daily during radiotherapy. The first dose of temozolomide will begin the day before the first fraction of radiation. The last dose will be taken the day of the last fraction of radiation. Following radiotherapy, maintenance temozolomide will be prescribed at the discretion of the treating neuro-oncologist.

1.2.8. How Supplied

Temozolomide capsules are made in 5 mg, 20 mg, 100 mg, and 250 mg doses.

1.2.9. Known Adverse Events

Adverse event	Concomitant Phase Radiotherapy + TEMODAR® (n=228)		Maintenance Phase TEMODAR® (n=224)	
	All	Grade ≥ 3	All	Grade ≥ 3
Alopecia	199 (69)	0	124 (55)	0
Fatigue	156 (54)	19 (7)	137 (61)	20 (9)
Nausea	105 (36)	2 (1)	110 (49)	3 (1)
Vomiting	57 (20)	1 (<1)	66 (29)	4 (2)
Anorexia	56 (19)	2 (1)	61 (27)	3 (1)

Headache	56 (19)	5 (2)	51 (23)	9 (4)
Constipation	53 (18)	3 (1)	49 (22)	0
Convulsions	17 (6)	10 (3)	25 (11)	7 (3)
Thrombocytopenia	11 (4)	8 (3)	19 (8)	8 (4)

1.2.10. Contraindications

Temozolomide is contraindicated in patients with hypersensitivity to temozolomide, any of the capsule components, or DTIC.

4.5 General Concomitant Medication and Supportive Care Guidelines

All supportive therapy for optimal medical care will be given during the study period at the discretion of the attending physician(s) within the parameters of the protocol.

- 4.5.1. Steroids may be given as clinically indicated. The total dose must be recorded pretreatment and at the time of each treatment evaluation. Steroids will be used in the smallest dose that will afford the patient satisfactory neurologic function and the best possible quality of life.
- 4.5.2. Antiemetics: Patients may be given antiemetics prior to each daily dose of temozolomide. The antiemetic and dosing will be left to the treating physician's discretion. Other antiemetics such as 5HT3 antagonists or lorazepam (Ativan®) may be used at the discretion of the investigator for late nausea and vomiting.
- 4.5.3. Anticoagulants: Patients who are taking warfarin (Coumadin®) may participate in this study; however, it is recommended that international normalization ration (INR) or prothrombin time be monitored carefully. The frequency of INR determinations is left to the clinical judgment of the investigator. Subcutaneous heparin or fractionated heparin products are also permitted.
- 4.5.4. Pneumocystis prophylaxis: Prophylaxis against *Pneumocystis carinii* pneumonia is typically recommended for all patients receiving concomitant temozolomide and radiotherapy for the 42-day regimen. Since the duration of radiotherapy/temozolomide regimen is shorter on this protocol, the use of pneumocystis prophylaxis is left to the clinical judgment of the investigator. All patients receiving temozolomide, particularly patients receiving steroids, should be observed closely for the development of *Pneumocystis* pneumonia. Acceptable regimens are:

4.5.4.1. *Trimethoprim-sulfamethoxazole*: Trimethoprim will be given at 160 mg/sulfamethoxazole 800 mg daily for 3 days each week, beginning on day 1 of radiation therapy and continuing for 14 days after completion of radiation therapy.

4.5.4.2. For subjects allergic to sulfa compounds, pentamidine (or dapsone or atovaquone) may be the drug used. The choice is left to the discretion of the investigator.

4.5.5. Infections are to be treated with the appropriate antibiotics and recorded.

4.5.6. Analgesics and any other medications are to be specified and their doses recorded.

4.5.7. Recall blisters post-sun exposure can be treated with Domeboro soaks. If neuropathy occurs, patients may be placed on gabapentin.

4.5.8. No other chemotherapy treatment is permitted during protocol treatment.

4.6 **Duration of Therapy**

The first dose of temozolomide will begin the day before the first fraction of radiation. It will be taken through the day of the last fraction of radiation. Following radiotherapy, maintenance temozolomide will be prescribed at the discretion of the treating neuro-oncologist.

4.7 **Duration of Follow Up**

Patient follow-up schedule is summarized under section 8. Study Calendar.

The following will be obtained at pre-treatment evaluation and at each follow-up time points: Neurologic history and physical examination, KPS, steroid use assessment, and toxicity evaluation (see Follow-up assessment form). MRI with gadolinium will be obtained pre-treatment and at 1, 6, and 12 months following treatment until progression is documented.

In addition to the follow-up schedule outlined in section 8, additional clinical follow-up and MRI scans will be obtained based on clinical progress during the first 12 months following radiation.

After the first 12 months or after the documentation of disease progression, patients will be followed every 3-6 months at the discretion of the treating physician.

For those subjects who are unable to come for clinic visits, clinical follow-up information will be obtained via 1) a phone call to the patient and/or 2) clinic source document from his/her local physician. For patients unable to return to for imaging studies, source documents from outside institutions will be used to document imaging follow-up.

4.8 **Criteria for Removal from Study**

- Disease progression or death
- Intercurrent illness that prevents further administration of treatment: a condition, injury, or disease unrelated to cancer, that renders continuing temozolomide or radiation treatment unsafe or regular study visits impossible, including, but not limited to, active infection, symptomatic congestive heart failure, unstable angina pectoris, cardiac arrhythmia, pregnancy, or psychiatric illness that would limit compliance with study requirements.
- Unacceptable adverse event(s) (see adverse events)
- Patient decides to withdraw from the study
- General or specific changes in the patient's condition that render the patient ineligible for the study
- Non-compliance with study medication or protocol-required evaluations and study visits
- Inability of subject to comply with study requirements
- Determination by the investigator that it is no longer safe for the subject to continue therapy
- Patients who inadvertently become pregnant
- At the discretion of the treating investigators

Subjects/patients may withdraw at any time or be dropped from the study at the discretion of the investigator should any untoward effects occur. In addition, a subject/patient may be withdrawn by the investigator if he/she violates the study plan or for administrative and/or other safety reasons. Any adverse experiences which are present at the time of discontinuation/withdrawal should be followed until resolution or stabilization.

Subjects who are discontinued from the study will still be followed for disease progression and survival.

If the reason for withdrawal from the trial is the death of the subject, the two options for categorizing withdrawal are either progressive disease or an adverse event (AE; more than one AE may be documented as a reason for withdrawal). Only one event will be captured as the cause of death. Note that death is an outcome and not an AE.

All trial treatment-related toxicities and SAEs must be followed up until resolution.

Subjects/patients who discontinue from the study for reasons unrelated to the study (e.g., personal reasons, or adverse events after registration but prior to receiving study therapy) may be replaced as required for the study to meet its objectives. The decision to remove a subject/patient and to replace dropouts will be made by the treating investigator. The replacement will generally receive the same treatment or

treatment sequence (as appropriate) as the allocation number replaced.

4.9 Alternatives

Alternative treatments include conventionally fractionated external beam radiotherapy with or without temozolomide or no therapy.

4.10 Compensation

Subjects will not be paid for their participation in the study.

5. DOSING DELAYS/DOSE MODIFICATIONS

Not applicable due to the short treatment duration of this study.

6. ADVERSE EVENTS AND REPORTING PROCEDURES

6.1 Potential Adverse Events

6.1.1. Radiation

6.1.1.1. Early, < 30 days from treatment: Expected adverse events include fatigue, alopecia, skin erythema, serous otitis, radiation pharyngitis, headache, neck pain, nausea and vomiting, and lethargy.

6.1.1.2. Late, > 30 days from treatment: Possible adverse events include focal neurologic deficits, memory difficulties, dementia, radiation necrosis, and radiation induced neoplasms.

6.1.2. Temozolomide

During the concomitant phase (temozolomide (TMZ) + radiotherapy) of the Stupp's trial(4), adverse reactions including thrombocytopenia, nausea, vomiting, anorexia, and constipation were more frequent in the TMZ + RT arm. The incidence of other adverse reactions was comparable between the arms with and without temozolomide. The most common adverse reactions across the cumulative TMZ experience were alopecia, nausea, vomiting, anorexia, headache, and constipation. Forty-nine percent (49%) of patients treated with TMZ reported one or more severe or life-threatening reactions, most commonly fatigue (13%), convulsions (6%), headache (5%), and thrombocytopenia (5%).

Number (%) of patients with adverse reactions:

	RT Alone	TMZ + conventional	Maintenance phase
--	----------	--------------------	-------------------

	n=285		RT; n=288		TMZ; n=224	
	All	Grade ≥3	All	Grade ≥3	All	Grade ≥3
General						
Anorexia	25 (9)	1 (<1)	56 (19)	2 (1)	61 (27)	3 (1)
Dizziness	10 (4)	0	12 (4)	2 (1)	12 (5)	0
Fatigue	139 (49)	15 (5)	156 (54)	19 (7)	137 (61)	20 (9)
Headache	49 (17)	11 (4)	56 (19)	5 (2)	51 (23)	9 (4)
Weakness	9 (3)	3 (1)	10 (3)	5 (2)	16 (7)	4 (2)
Central Nervous System						
Confusion	12 (4)	6 (2)	11 (4)	4 (1)	12 (5)	4 (2)
Convulsions	20 (7)	9 (3)	17 (6)	10 (3)	25 (11)	7(3)
Memory Impairment	12 (4)	1 (<1)	8 (3)	1 (<1)	16 (7)	2 (1)
Eye						
Vision Blurred	25 (9)	4 (1)	26 (9)	2 (1)	17 (8)	0
Immune						
Allergic Reaction	7 (2)	1 (<1)	13 (5)	0	6 (3)	0
Gastrointestinal						
Abdominal pain	2 (1)	0	7 (2)	1 (<1)	11 (5)	1 (<1)
Constipation	18 (6)	0	53 (18)	3 (1)	49 (22)	0
Diarrhea	9 (3)	0	18 (6)	0	23 (10)	2 (1)
Nausea	45 (16)	1 (<1)	105 (36)	2 (1)	110 (49)	3 (1)
Stomatitis	14 (5)	1 (<1)	19 (7)	0	20 (9)	3 (1)
Vomiting	16 (6)	1 (<1)	57 (20)	1 (<1)	66 (29)	4 (2)
Injury						
Radiation injury NOS	11 (4)	1 (<1)	20 (7)	0	5 (2)	0
Musculoskeletal						
Arthralgia	2 (1)	0	7 (2)	1 (<1)	14 (6)	0
Platelet						
Thrombocytopenia	3 (1)	0	11 (4)	8 (3)	19 (8)	8 (4)
Psychiatric						
Insomnia	9 (3)	1 (<1)	14 (5)	0	9 (4)	0
Respiratory						
Coughing	3 (1)	0	15 (5)	2 (1)	19 (8)	1 (<1)
Dyspnea	9 (3)	4 (1)	11 (4)	5 (2)	12 (5)	1 (<1)
Skin						
Alopecia	179 (63)	0	199 (69)	0	124 (55)	0
Dry skin	6 (2)	0	7 (2)	0	11 (5)	1 (<1)
Erythema	15 (5)	0	14 (5)	0	2 (1)	0
Pruritus	4 (1)	0	11 (4)	0	11 (5)	0
Rash	42 (15)	0	56 (19)	3 (1)	29 (13)	3 (1)

Other						
Taste perversion	6 (2)	0	18 (6)	0	11 (5)	0

